2.4.3 Exploratory endpoints

There are no planned exploratory endpoints, however, had the trial continued to full enrolment, an exploratory analysis would have compared the primary endpoint between the two intervention arms (conservative management plus fludrocortisone and conservative management plus midodrine).

2.5 Study assessments

Participants are assessed at three, six and 12 months from trial entry. As this is a pragmatic trial, assessments can take place within +/- 4, 6 and 8 weeks for the three, six and 12 month visits respectively. A simplified schedule of assessment is given in **Table 1**.

		Visit			
Form		Month 3	Month 6	Month 12	
	Baseline	(+/- 4 weeks)	(+/- 6 weeks)	(+/- 8 weeks)	
Demographics	Х				
Medical History	Х				
UPDRS*	Х				
Blood pressure	Х	Х	Х	Х	
Culprit medication review	Х	Х	Х	Х	
ОНQ	Х	Х	Х	Х	
NEADL	Х	Х	Х	х	
EQ-5D-5L	Х	Х	Х	Х	
Falls diary return		Х	Х	Х	
Hospital admission review		Х	Х	Х	

Table 1: Simplified schedule of assessments

*Only for participants with Parkinson's disease, Dementia with Lewy bodies or Multi System Atrophy

2.6 Sample size and power

The trial was designed to test two null hypotheses:

- I. The mean difference in six-month OHQ score between conservative management plus fludrocortisone and conservative management alone is = 0
- II. The mean difference in six-month OHQ score between conservative management plus midodrine and conservative management alone is = 0

Using standard sample size formula for a two sample t-test, a three-arm trial without an interim analysis would require 103 participants per arm to detect a difference of 1.0 point on the OHQ with 90% power, a two-sided type I error of 5% (equivalently a one-sided type I error of 2.5%), and assuming a standard deviation of 2.2.

A difference of 1.0 point on the OHQ is used as this represents an established minimally clinically important difference (MCID) [1] and was confirmed following discussion with patient and public involvement (PPI) representatives. A standard deviation of 2.2 was assumed based on local audit data from a cohort of 100 neurogenic and non-neurogenic patients.

Assuming attrition of 15% (based on comparable clinical trials in older people of similar duration [6,7] the recruitment target was 366 (122 per arm).

If at the interim analysis an intervention arm showed no benefit compared to the control arm (i.e. if the estimated mean OHQ score at 6 months was worse than control) it would be recommended to be dropped from the study. The multi-arm design would control the one-sided family-wise error rate (FWER), the total chance of falsely recommending an ineffective treatment, at 4.5%. With the possibility of early lack-of-benefit stopping, the FWER would be lower than this. The pair-wise error rate (PWER) would be controlled at 2.5% for each comparison.

Taking into account the interim analysis, which would be conducted once 200 participants had been recruited, the power of the design to recommend each treatment is displayed in the table below (as determined from one million simulation replicates per scenario).

We assumed participants would be recruited at a rate of 0.8 per site per month over a 30-month period with a staggered opening of sites (six sites open for the first six months with two new sites opening per month from month 7 onwards until a total of 20 sites are open). Under this assumed pattern of recruitment we would expect around 150 and 100 participants to have reached the three and six month follow-up time points respectively. The below table assumes only participants with six month data collected are included in the interim analysis. In practice including participants with three-month data but not yet six-month data would allow modest additional efficiency.

Scenario	Probability recommend fludrocortisone	Probability recommend midodrine	Probability recommend both	Probability recommend at least one
Mean effect of both = 0 (null scenario)	2.4%	2.4%	0.4%	4.4%
Fludrocortisone has MCID, midodrine effect = 0	91.8%	2.5%	2.5%	91.8%
Midodrine has MCID, fludrocortisone effect = 0	2.4%	91.7%	2.4%	91.7%
Both treatments have MCID effect	89.9%	89.7%	82.8%	96.8%

R code used to perform the power calculations can be found in *S*:\School Statistics\NCTU\CONFORM-OH\2. Study design\2.1 Statistical considerations\Sample size calculation

3. STATISTICAL CONSIDERATIONS

3.1 Timing of final analysis

The final analysis will take place once the last 12-month follow-up visit is complete. Once all data queries have been resolved (as far as possible) the database will be locked and the final analysis will commence.

3.2 Interim analyses, stopping guidelines and data monitoring

Had the trial continued past the internal pilot phase an interim analysis would have been performed based on available three and six month primary outcome data following recruitment of the 200th participant.

Analysis methods which would have been followed for the interim analysis can be found in the Appendix.

The DMC will meet periodically to review progress of the trial and the safety of trial participants. Further detail on the roles and responsibilities of the DMC can be found in the current version of the DMC charter. The DMC will have access to unblind outcome data. With the exception of the interim analysis time point (which will no longer be reached), outcome data will be summarised descriptively and no formal analyses will be conducted.

3.3 Confidence intervals and p-values

Had the trial continued to full enrolment all statistical tests for the final analysis would have been 2-sided and performed using a 5% significance level. For the interim analysis, an experimental arm would have been recommended to be dropped if the estimated mean between-group difference for an experimental arm is ≥ 0 (corresponding to the arm having worse outcome than control). This is equivalent to a one-sided p-value of >0.5.

Given that the trial has ended early no statistical testing will be performed. Any confidence intervals will be reported at the 95% level.

3.4 Analysis sets

The following analysis sets will be defined:

Analysis Set 1	 Participants will be analysed according to the treatment group they were randomised to receive, i.e. following the intention-to-treat (ITT) principle All available outcome data will be included in the analysis
Analysis Set 2	 Participants will be analysed according to the treatment group they were randomised to receive, i.e. following the intention-to-treat (ITT) principle Outcome data following cross-over to an alternative treatment group, or discontinuation of allocated trial treatment, will be set to missing
Safety Analysis Set (SAS)	 For each treatment group, the Safety Analysis Set will comprise all participants exposed to that treatment strategy Safety data (adverse events) will be summarised according to the treatment strategy received at the time of onset of each adverse event. Participants who cross-over between treatment groups will be included in the Safety Analysis Set for each treatment group

Primary and secondary clinical outcome measures will be reported according to randomised treatment group; safety data will be reported according to the treatment strategies received. Analysis Set 1 will be the main analysis set used to report the primary and secondary clinical outcome measures. Analysis Set 2 may also be used to provide supplementary information on the primary outcome measure. All safety data will be reported using the Safety Analysis Set.

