5.4.2 Follow-up Visits (Three, six and 12 Months)

The clinical/ research team will schedule the three-, six- and 12-month follow-up clinic appointments with all participants. These should be face-to-face, if possible; however, remote follow-up visits are acceptable. This is a pragmatic study so some variability in the timing of follow-up assessments is acceptable (see schedule of Events for follow-up windows).

All participants will have their supine and nadir standing BP taken or provide self-recorded BP measurements if follow-up is remote (acceptable methods for obtaining BP measurements are listed in Section 5.5.1).

Blood tests will be carried out/arranged as part of their usual clinical care (see Schedule of Events).

At the three-month follow-up participants who were randomised to receive IMP will be asked to confirm that they have started the prescribed IMP.

Participants will be asked to either provide their falls diary at each follow-up visit or provide details from their falls diary over the phone when they speak to the site research team member or clinician. At each consultation, participants will be reminded to complete their falls diary and bring it with them to their next face-to-face follow-up visit or have it to hand to allow the information to be provided over the phone/video call. If participants forget to bring their falls diaries to their face-to-face consultation or are unable to attend face-to-face consultations this data can be collected over the phone and a new diary can be posted out with a self-addressed envelope for return of the partially completed diary to enable timely data collection.

Participants will be required to complete the OHQ, EQ-5D-5L, Nottingham Extended ADL Scale and the Health and Social Service Use questionnaire. Additionally, participants will complete a Time and Travel Questionnaire at the six-month follow-up consultation. For remote visits, these questionnaires will be completed by the clinician over the phone/videoconference with the participant.

Data regarding adherence to trial intervention, culprit medications and Adverse Events will be collected and recorded in the CRF.

For sites who carry out face-to-face follow-up with patients in the community as routine practice, these consultations can be scheduled at the participant's home. However, a medically qualified, GMC registered clinician must retain oversight.

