6.9.1 Cross-over and Treatment Withdrawal

During the course of the study, the clinical team may consider crossing over of treatment arms, if they judge clinically that a treatment is not working. The same consideration may be made for combination treatments. While we will not seek to dictate clinical decisions, we ask the clinical teams to allow sufficient time (at least four weeks) on maximum tolerated dose, and ideally until the primary outcome is assessed at six months, before considering changing allocated treatment.

If allocated study treatment changes during the trial, details of the changes, including when, by whom and why the decision was made should be recorded in the eCRF.

Participants will not be withdrawn from the trial if treatment contamination, cross-over or withdrawal occurs, but will remain in the trial and be offered all follow-up data collection visits as part of the intention-to-treat analysis.

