7.2 Recording Adverse Events and Adverse Reactions (AEs and ARs)

All AEs and ARs will be recorded from the date of randomisation until completion of 12-month visit or until the participant withdraws. Participants will be asked about AEs and ARs at each scheduled study visit.

All AEs and ARs (unless listed below in 7.3) will be recorded in the participants' medical notes and the data entered onto the AE page in the electronic case report form (eCRF). The local site PI's clinical judgement should be used to determine if an AE is reportable as an AR.

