8 STATISTICAL CONSIDERATIONS

8.1 Analysis Populations

The following analysis populations will be defined:

Analysis population	Definition
Efficacy Analysis Population 1 - Intention-to-treat (ITT)	
 Participants will be analysed according to their randomised treatment group, i.e. following the ITT principle All available outcome data will be included in the analysis
Efficacy Analysis Population 2	
 Participants will be analysed according to their randomised treatment group Outcome data following cross-over to another treatment group, or discontinuation of allocated treatment, will be set to missing
Safety population	
 For each treatment group, all participants exposed will be included in the safety population Safety data will be summarised according to the treatment strategy received at the time of onset of each AE

The primary outcome will be analysed in the intention-to-treat population with sensitivity analyses in the per-protocol population. Secondary outcomes will be analysed in the intention-to-treat population. Safety data will be reported in the safety population.

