6. SAFETY

6.1 Adverse Events

Safety data will be reported in the Safety Analysis Set, with adverse events reported according to treatment received at the time of AE onset.

The following metrics will be used to provide an overall summary of adverse events reported while exposed to each treatment group, see Example Table 10:

- The number of participants exposed to each treatment group.
- The total exposure time (measured in years) to each treatment group, i.e. a sum across all participants of the amount of time they were exposed to each treatment group.
- Number and proportion of participants affected by at least one adverse event while exposed to each treatment group. Percentages will be calculated out of those exposed.
- Worst grade (mild, moderate, severe) adverse event reported while exposed to each treatment group. This will be tabulated with percentages calculated out of those exposed.
- Total number of adverse event occurrences reported by each participant while exposed to each treatment group. This will be tabulated (with percentages calculated out of those exposed) and/or reported as median and range, as appropriate
- Total number of unique adverse event occurrences (i.e. different preferred terms) reported by each participant while exposed to each treatment group. This will be tabulated (with percentages calculated out of those exposed) and/or reported as median and range, as appropriate
- Total number of adverse event occurrences reported across all participants while exposed to each treatment group. This will also be broken down by severity (mild, moderate, severe).
- The incidence rate (IR) of adverse event occurrence while exposed to each treatment group (i.e. total number of AE occurrences / total exposure time).

For each adverse event, at the preferred term level, we will also report the following metrics by treatment group, see Example Table 11:

- The number and proportion of participants experiencing the adverse event at any point while exposed to each treatment group. Percentages will be calculated out of those exposed.
- The worst reported severity (mild, moderate, severe) for the adverse event at any point while exposed to each treatment group. Percentages will be calculated out of those exposed.
- The total number of occurrences of the adverse event while exposed to each treatment group.
- The total number of occurrences of the adverse event, by severity (mild, moderate, severe), while exposed to each treatment group.

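### Safety is tabulated only by treatment received at event onset, with no rule for pre-dose, post-stop or combination time, so the percentage and adverse-reaction tables can mislead

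*SAP*

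**What the plan says.** Protocol 8.1 and SAP 3.4 use the same rule. The SAP wording is "Safety data (adverse events) will be summarised according to the treatment strategy received at the time of onset of each adverse event", and the Protocol has "Safety data will be summarised according to the treatment strategy received at the time of onset of each AE". Membership of the set follows exposure: "For each treatment group, the Safety Analysis Set will comprise all participants exposed to that treatment strategy". For treatment changes, "Participants who cross-over between treatment groups will be included in the Safety Analysis Set for each treatment group". SAP 3.4 sends all safety data to this set.

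SAP 6.1 reports, among other things, the "Number and proportion of participants affected by at least one adverse event while exposed to each treatment group", with everyone exposed as the denominator and no minimum exposure. It also gives total exposure time and an incidence rate per treatment. Adverse reactions and non-serious events get the same summaries. SAP 6.2 applies the same denominator to serious adverse events and adds a line listing (Example Table 12).

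Collection begins before any drug is taken. Protocol 7.2: "All AEs and ARs will be recorded from the date of randomisation until completion of 12-month visit". Protocol 5.3 asks for the drug to be started promptly but fixes no day. Under Protocol 5.4.2, at the three-month visit, "participants who were randomised to receive IMP will be asked to confirm that they have started the prescribed IMP". On adding the other drug, Protocol 6.9.1 says: "The same consideration may be made for combination treatments". Example Tables 10 and 11 have three columns only: control, fludrocortisone and midodrine.

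**The concern.** The safety objective (SAP 1.2.2, item 4) asks how each drug strategy compares with conservative management alone. Conservative management is the background of all three strategies. Someone who stops a drug and goes back to it is therefore, on the SAP's own terms, exposed to the control strategy.

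Three things follow.

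1. The control column gains people from the drug arms whose exposure is short and who are there because they stopped. Example Table 3 lists side effects as a reason for stopping. In a percentage of those exposed, each of them counts as a whole person.
2. There is no lag. An event that a site judges related to a drug, but that begins after the last dose, is classified by the strategy in use on that day. In the adverse-reaction table it can then appear outside the column of the drug thought to have caused it.
3. Events on both drugs have no column of their own, and nothing says whether to count them twice or place them under one drug.

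No summary table of adverse events, reactions or serious events by randomised arm is planned. No set of columns therefore keeps the protection of randomisation.

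**Working it through.** The plan states no figure to reproduce, so this is a reading of the rules followed by an illustration.

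**Where each period goes under the text**

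| Period | What the documents say |
|---|---|
| Drug arm, before first dose | Events are recorded (Protocol 7.2); no column is assigned |
| Drug arm, stopped, back on conservative management | A listed switch (Example Table 3); in the set of each group (SAP 3.4), so control |
| Event after last dose | Strategy at onset; no lag (SAP 3.4, 6.1) |
| Both drugs together | Foreseen (Protocol 6.9.1); no column (Example Tables 10, 11) and no row (Example Table 3) |

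**Percentages, stoppers only, no drug effect**

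Inputs: 122 per arm and 12 months from the documents. Assumptions: a constant event rate λ in every state; a fraction d of each drug arm stops at three months; all stoppers return to conservative management. Pre-dose time is left out, because the SAP does not place it.

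- Risk over time t: 1 − exp(−λt).
- Control column: [(1 − e^(−λ)) + 2d(1 − e^(−0.75λ))] / (1 + 2d).
- Each drug column: (1 − d)(1 − e^(−λ)) + d(1 − e^(−0.25λ)).

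For λ = 1 and d = 0.3, the control denominator is 122 + 2 × 0.3 × 122 = 195.2.

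- Control: (122 × 0.632 + 73.2 × 0.528) / 195.2 = 59.3%.
- Drug: 0.7 × 0.632 + 0.3 × 0.221 = 50.9%.

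| λ per year | d | By randomised arm | Control column | Drug column |
|---|---|---|---|---|
| 1.0 | 10% | 63.2% | 61.5% | 59.1% |
| 1.0 | 30% | 63.2% | 59.3% | 50.9% |
| 1.0 | 40% | 63.2% | 58.6% | 46.8% |
| 0.5 | 10% | 39.3% | 38.0% | 36.6% |
| 0.5 | 40% | 39.3% | 35.8% | 28.3% |

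The spurious gap runs from about 1 to 12 percentage points and makes the drugs look safer. Arm size cancels from these expected percentages; in a small trial, chance variation comes on top.

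**Incidence rates, with a true drug effect**

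Assumptions: control rate 2 per person-year; true on-drug rate ratio R of 1.5 to 3; d of 10% to 40% stopping at month three; the raised rate persists for 14 or 30 days after stopping; a 14-day pre-dose interval is counted as control.

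Example with R = 2, d = 0.2 and 30 days:

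- Off-drug time: 244 × 0.2 × 0.75 = 36.6 person-years.
- Pre-dose time: 244 × 14/365.25 = 9.35 person-years.
- Control person-time: 122 + 36.6 + 9.35 = 167.95.
- Carry-over time: 244 × 0.2 × 30/365.25 = 4.01.
- Control rate: 2 × (167.95 + 4.01) / 167.95 = 2.048.
- Observed ratio: 4 / 2.048 = 1.95.

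Over the grid, 1.5 becomes 1.47 to 1.50, 2.0 becomes 1.93 to 1.99, and 3.0 becomes 2.78 to 2.96. Without the pre-dose interval the largest dilution is nearly the same: in the 40%, 30-day case, carry-over is 97.6 × 30/365.25 = 8.02 person-years out of 122 + 73.2 = 195.2, so 2.0 becomes 2 / (1 + 8.02/195.2) = 1.92. With no drug effect the ratio is exactly 1.

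**The case against.** Reporting by treatment received is a recognised choice for safety, and both documents pre-specify it consistently. A table by randomised arm alone would dilute drug harms when cross-over is allowed. SAP 6.1 already plans the exposure-adjusted rate, which copes well with unequal exposure. SAP 3.3 rules out statistical testing, and SAP 6.1 keeps relative risks for adverse events to the full-enrolment case. Example Table 12 shows randomised group, drug at onset, drug dates and onset date, so reportable serious events can be traced. Falls, syncope, fall injuries and hospital admissions are reported by randomised group (SAP 5.2). All of this stands, and it limits the point to the percentage and adverse-reaction tables. It does not fill the gaps: no listing with those fields is planned for non-serious events, and a descriptive table can still be misread.

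A reader might go further and infer that every drug-arm participant awaiting a first dose is an exposed control. A two-week wait by all 244, with no stopping and λ = 1, would then give a control column of 366 with 23.6% affected, against 61.8% on drug. The documents do not support this. SAP 3.4 places people in more than one set when they cross over, and waiting is not crossing over. Time before the first dose can equally be read as time on the allocated strategy, Protocol 5.3 asks for a prompt start, and a column of 366 describes a fully enrolled trial. The sound statement is that pre-dose time is unassigned. Nor does it follow that the comparison by treatment received is wrong in itself.

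**Conclusion.** The point holds as a minor one. The Safety Analysis Set is under-specified for pre-dose, post-stop and combination time. Percentages of those exposed are not comparable between columns when exposure lengths differ, and the onset rule without a lag can move a drug reaction out of that drug's column. That stoppers enter the control column rests on the cross-over rule in SAP 3.4 read with the switch rows of Example Table 3; the SAP does not spell it out.

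The actual size is unknown. The documents give no observed stopping, waiting or event rates, so every figure above other than 122 per arm and 12 months depends on assumptions. Those figures also assume that stoppers have the same underlying event rate as everyone else, which selection through side effects may break. Within those limits, percentages can differ by several points with no drug effect, while incidence rates shift little. The trial closed early and its safety reporting is descriptive, so no inferential conclusion is at risk.

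**What to change.** In SAP 3.4, 6.1 and 6.2:

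- Add adverse event, adverse reaction and serious adverse event tables by randomised arm (Analysis Set 1) alongside the tables by treatment received.
- In the latter, state where time before the first dose, time after stopping and time on both drugs belong, and add a combined-drug column.
- Pre-specify a lag after the last dose, and show results with and without it.
- Base any comparison between these columns on the incidence rate already planned, not on the percentage of those exposed.

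The cost is some SAP wording and one extra set of tables from data already collected. The drawback is thin cells, given the small numbers. None of this changes how participants are treated.
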